3.3 Trial Population

The trial population will consist of eligible subjects who, in the investigator's judgment, could potentially benefit from adjunctive treatment with brexpiprazole for MDD according to the following criteria:

- Subjects who participated in Trial 331-10-227, Trial 331-10-228 or Trial 331-13-214 will be eligible for Trial 331-10-238 if they meet one of the following conditions:
 - Subjects who completed participation in the double-blind randomization phase (ie, Week 14 visit of phase B) in Trial 331-10-227, Trial 331-10-228 or Trial 331-13-214 or
 - Subjects who continued into Phase A+ (were not randomized into Phase B) at the end of prospective treatment (ie, Week 8 visit of Phase A) in Trial 331-10-227, Trial 331-10-228 or Trial 331-13-214, **BUT DID NOT** meet criteria for remission (defined as a MADRS Total Score of ≤ 10) at the Week 14 visit of Phase A+ in Trial 331-10-227, Trial 331-10-228 or Trial 331-13-214.
- Subjects who participated in a double-blind phase 3 brexpiprazole MDD trial will be eligible for the 331-10-238 trial if they have completed the last scheduled visit of the double-blind phase 3 trial.
- Subjects must qualify for Trial 331-10-238 at the last scheduled visit of the prior double-blind phase 3 trial and must be able to continue therapy without interruption between the double-blind and open-label trials. Based on the projected enrollment estimates for the prior double-blind phase 3 brexpiprazole MDD trials, up to approximately 3,000 subjects may enroll into Trial 331-10-238.

3.4 Eligibility Criteria

3.4.1 Informed Consent

Written informed consent will be obtained from all subjects (or their guardian or legal representative, as applicable for local laws). Consent will be documented on a written ICF. The ICF will be approved by the same Institutional Review Board/Independent Ethics Committee (IRB/IEC) that approves this protocol. Each ICF will comply with the FDA regulations in 21 Code of Federal Regulations (CFR) Part 50, International Conference on Harmonization Good Clinical Practice (ICH GCP), and local regulatory requirements. The investigator agrees to obtain approval from the sponsor of any written ICF used in the trial, prior to submission to the IRB/IEC.

Investigators may discuss trial availability and the possibility for entry with a potential subject without first obtaining consent. However, informed consent must be obtained and documented prior to initiation of any procedures that are performed solely for the purpose of determining eligibility for this trial, including withdrawal from current medication(s). The ICF for the open-label trial may be provided to potential candidates for review and discussion toward completion of the prior double-blind phase 3 trial, but the form must not be signed until the day of the Screening/Baseline visit for Trial 331-10-238 (ie, the last scheduled visit of the prior double-blind phase 3 trial).

Once appropriate essential information has been provided and fully explained in layman's language to the subject by the investigator (or a qualified designee), the IRB/IEC-approved written ICF will be signed and dated by both the subject and the person obtaining consent (investigator or designee), as well as by any other parties required by the IRB/IEC. The subject will receive a copy of the signed ICF; the original shall be kept on file by the investigator.

In addition to the English version of the ICF, the document may also be translated by the central translation vendor into local languages for use in this trial. Translation with back-translation for confirmation will be utilized to ensure accuracy.

3.4.2 Inclusion Criteria

Subjects are required to meet the following inclusion criteria:

Table 3.4.2-1 Inclusion Criteria	
	All Subjects
1.	Subjects who are able to provide written informed consent and/or consent obtained from a legally acceptable representative (as required by IRB/IEC) prior to the initiation of any protocol-required procedures.
2.	Ability, in the opinion of the principal investigator, to understand the nature of the trial and follow protocol requirements, including the prescribed dosage regimens, tablet/capsule ingestion, and discontinuation of prohibited concomitant medication; to read and understand the written word in order to complete subject-reported outcomes measures; and to be reliably rated on assessment scales.
3	Male and female outpatients 18 to 65 years of age, inclusive, at the time of informed consent for Trial 331-10-238.
4	Subjects willing to discontinue all prohibited psychotropic medications starting from the time of signing the ICF and during the trial period (refer to Section 4).

Table 3.4.2-1 Inclusion Criteria	
	331-10-227, 331-10-228 and 331-13-214 Subjects Only
5.	Subjects who, in the opinion of the investigator, could potentially benefit from administration of brexpiprazole as adjunctive therapy to their antidepressant therapy and who meet one of the following criteria: a) Subjects who completed participation in the double-blind randomization phase (ie, Week 14 visit of Phase B) in Trial 331-10-227, Trial 331-10-228 or Trial 331-13-214 or b) Subjects who continued into Phase A+ (were not randomized into Phase B) at the end of prospective treatment (ie, Week 8 visit of Phase A) in Trial 331-10-227, Trial 331-10-228 or Trial 331-13-214, BUT DID NOT meet criteria for remission (defined as a MADRS Total Score of ≤ 10) at the Week 14 visit of Phase A+ in Trial 331-10-227, Trial 331-10-228 or Trial 331-10-227, Trial 331-10-228 or Trial 331-13-214...
Eligible Subjects From Other Double-Blind Phase 3 Brexpiprazole MDD Trials	
6.	Subjects who completed the last scheduled visit of the prior double-blind phase 3 trial, and who in the opinion of the investigator, could potentially benefit from administration of brexpiprazole as adjunctive therapy to their antidepressant therapy.

3.4.3 Exclusion Criteria

Subjects entering the open-label trial at the last scheduled visit of the prior double-blind phase 3 trial will be excluded from Trial 331-10-238 if they meet any of the following exclusion criteria.

Table 3.4.3-1 Exclusion Criteria	
Sex and Reproductive Status	
1.	Sexually active females of childbearing potential (see Section 5.5) and male subjects who are not practicing two different methods of birth control with their partner during the trial and for 30 days after the last dose of trial medication or who will not remain abstinent during the trial and for 30 days after the last dose. If employing birth control, each couple must use two of the following precautions: vasectomy, tubal ligation (subject or partner), vaginal diaphragm, IUD, birth control pill, birth control implant, birth control depot injections, condom, or sponge with spermicide.
2.	Females who are breast-feeding and/or who have a positive pregnancy test result prior to receiving open-label brexpiprazole in Trial 331-10-238.
Administrative	
3.	Subjects with a major protocol violation during the course of their participation in the prior double-blind phase 3 trial. Minor violations such as occasional visits outside of the acceptable window or a missing blood draw will not exclude a subject from participation in Trial 331-10-238; however, continual lack of compliance with the visit schedule, trial assessments, or treatment regimen in the prior double-blind phase 3 trial would be considered a major violation that would result in exclusion from Trial 331-10-238. The medical monitor should be contacted if the investigator is unsure of a subject's eligibility.
Target Disease	
4.	Subjects who have received ECT for the current depressive episode.
5.	Subjects who have had an inadequate response to ECT at any time in the past or who have had a vagus nerve stimulation or deep brain stimulation device implanted at any time for management of treatment-resistant depression. Subjects who have had Transcranial Magnetic Stimulation during the current major depressive episode.
6.	Subjects with a current need for involuntary commitment or who have been hospitalized during the prior double-blind phase 3 trial for the current major depressive episode.

Table 3.4.3-1 Exclusion Criteria	
7.	Subjects with a current Axis I (DSM-IV-TR) diagnosis of: 
 • Delirium, dementia, amnestic or other cognitive disorder • Schizophrenia, schizoaffective disorder, or other psychotic disorder • Bipolar I or II disorder • Eating disorder (including anorexia nervosa or bulimia) • Obsessive compulsive disorder • Panic disorder • Post-traumatic stress disorder
8.	Subjects with a current Axis II (DSM-IV-TR) diagnosis of borderline, antisocial, paranoid, schizoid, schizotypal or histrionic personality disorder.
9.	Subjects experiencing hallucinations, delusions or any psychotic symptomatology in the current depressive episode.
10.	Subjects receiving new onset psychotherapy (individual, group, marriage, or family therapy) during the prior double-blind phase 3 trial.
Medical History and Concurrent Diseases	
11.	Subjects with a response of “Yes” on the C-SSRS Suicidal Ideation Item 4 (Active Suicidal Ideation with Some Intent to Act, Without Specific Plan) at entry, OR Subjects with a response of “Yes” on the C-SSRS Suicidal Ideation Item 5 (Active Suicidal Ideation with Specific Plan and Intent) at entry, OR Subjects with a response of “Yes” on any of the 5 C-SSRS Suicidal Behavior Items (actual attempt, interrupted attempt, aborted attempt, preparatory acts, or behavior) at entry, OR Subjects who, in the opinion of the investigator (including consideration of responses on the C-SSRS throughout the prior double-blind phase 3 trial), present a serious risk of suicide. Note: “Entry” is defined as the last scheduled visit of the prior double-blind phase 3 trial.
12.	Subjects who have met DSM-IV-TR criteria for substance abuse or dependence within the past 180 days; including alcohol and benzodiazepines, but excluding caffeine and nicotine.
13.	Subjects with hypothyroidism or hyperthyroidism (unless condition has been stabilized with medications for at least the past 90 days) and/or an abnormal result for free T4 at screening/baseline. Eligibility of subjects excluded based on an abnormal free T4 result can be discussed with the medical monitor if, in the investigator’s judgment, the subject is a suitable candidate for the trial.
14.	Subjects who currently have clinically significant neurological, hepatic, renal, metabolic, hematological, immunological, cardiovascular, pulmonary, or gastrointestinal disorders such as any history of myocardial infarction, congestive heart failure, HIV seropositive status/acquired immunodeficiency syndrome, chronic hepatitis B or C. Medical conditions that are minor or well-controlled may be considered acceptable if the condition does not expose the subject to an undue risk of a significant adverse event or interfere with assessments of safety or efficacy during the course of the trial. The medical monitor should be contacted in any instance where the investigator is uncertain regarding the stability of a subject’s medical condition(s) and the potential impact of the condition(s) on trial participation.
15.	Subjects with IDDM (ie, any subjects using insulin) are excluded. Subjects with non-IDDM may be eligible for the trial if their condition is stable as determined by satisfying ALL of the following criteria: 
 • Screening/baseline HbA1c < 7.0%, AND • Screening/baseline fasting glucose must be ≤ 125 mg/dL, AND • Subject has been maintained on a stable regimen of oral anti-diabetic medication(s) or diabetes has been well-controlled by diet during the prior double-blind phase 3 trial, AND • Subject has not had any hospitalizations due to diabetes or complications related to diabetes during the prior double-blind phase 3 trial, AND • Subject’s diabetes is not newly diagnosed during screening/baseline for Trial 331-10-238. Continuation of subjects excluded based on abnormal laboratory test results from the

Table 3.4.3-1 Exclusion Criteria	
	screening/baseline visit should be discussed with the medical monitor, if in the investigator's judgement the subject is a suitable candidate for the trial.
16.	Subjects with uncontrolled hypertension (DBP > 95 mmHg) or symptomatic hypotension, or orthostatic hypotension which is defined as a decrease of ≥ 30 mmHg in SBP and/or a decrease of ≥ 20 mmHg in DBP after at least 3 minutes standing compared to the previous supine blood pressure, OR development of symptoms.
17.	Subjects with known ischemic heart disease or history of myocardial infarction, congestive heart failure (whether controlled or uncontrolled), angioplasty, stenting, or coronary artery bypass surgery.
18.	Subjects with epilepsy or a history of seizures, except for a single seizure episode, for instance childhood febrile seizure, post traumatic, or alcohol withdrawal.
Physical and Laboratory Results	
19.	Subjects with a positive drug screen for cocaine, marijuana, or other illicit drugs are excluded and may not be retested or rescreened. Subjects with a positive urine drug screen resulting from use of prescription or OTC medications or products that in the investigator's documented opinion do not signal a clinical condition that would impact the safety of the subject or interpretation of the trial results may continue evaluation for the trial following consultation and approval by the medical monitor.
20.	
The following Screening/baseline laboratory test and ECG results are exclusionary:
 
1) Platelets $\leq 75,000/\text{mm}^3$ 2) Hemoglobin $\leq 9 \text{ g/dL}$ 3) Neutrophils, absolute $\leq 1000/\text{mm}^3$ 4) AST $> 2 \times \text{ULN}$ 5) ALT $> 2 \times \text{ULN}$ 6) CPK $> 3 \times \text{ULN}$, unless discussed with and approved by the medical monitor 7) Creatinine $\geq 2 \text{ mg/dL}$ 8) HbA1c $\geq 7.0\%$ 9) Abnormal free T₄, unless discussed with and approved by the medical monitor. (Note: Free T₄ is measured only if result for TSH is abnormal.) 10) QTcF $\geq 450 \text{ msec}$
 
NOTE: In addition, subjects should be excluded if they have any other abnormal laboratory tests, vital sign results, or ECG findings which in the investigator's judgment are medically significant and that would impact the safety of the subject or the interpretation of the trial results. Criteria are provided in Appendix 3, Appendix 4, and Appendix 5 to assist investigators in their assessments of results that may be potentially medically significant, depending on the subject's medical history and clinical presentation. Eligibility should be based on the Screening/baseline laboratory test and ECG results. The medical monitor should be contacted if the investigator is unsure of a subject's eligibility. Continuation of subjects excluded based on abnormal laboratory test and ECG results should be discussed with the medical monitor, if in the investigator's judgement, the subject is a suitable candidate for the trial.

Prohibited Therapies or Medications	
21.	Subjects who would be likely to require prohibited concomitant therapy during the trial (see Table 4.1-1 ^a).
Allergies and Adverse Drug Reactions	
22.	Subjects with a history of neuroleptic malignant syndrome or serotonin syndrome.
23.	Subjects with a history of true allergic response (ie, not intolerance) to more than one class of medications.

Table 3.4.3-1 Exclusion Criteria	
Other	
24.	Prisoners or subjects who are compulsorily detained (involuntarily incarcerated) for treatment of either a psychiatric or physical (eg, infectious disease) illness must not be enrolled into this trial.
25.	Any subject who, in the opinion of the investigator, should not participate in the trial.

ALT = alanine transaminase; AST = aspartate transaminase; CPK = creatine phosphokinase; C-SSRS = Columbia-Suicide Severity Rating Scale; DBP = diastolic blood pressure; DSM-IV-TR = *Diagnostic and Statistical Manual of Mental Disorders*, Fourth Edition, Text Revision; HbA1c = glycosylated hemoglobin; HIV = human immunodeficiency virus; IDDM = insulin-dependent diabetes mellitus; IUD = intrauterine device; NMS = neuroleptic malignant syndrome; OTC = over-the-counter; QTcF = QT interval as corrected for heart rate by Fridericia's formula; SBP = systolic blood pressure; T₄ = thyroxine; TSH = thyroid-stimulating hormone; ULN = upper limit of normal.

^aUse of CYP2D6 inhibitors or CYP3A4 inhibitors and inducers is prohibited during the trial. Fluoxetine, paroxetine, and duloxetine are protocol-defined ADTs that are also CYP2D6 inhibitors. In order to limit the potential higher exposure of brexpiprazole when coadministered with such inhibitors, the upper limit of the therapeutic ADT dose is limited to 40 mg for fluoxetine, 50 mg for paroxetine CR, and 60 mg for duloxetine.

Subjects who do not qualify for the open-label trial at the Screening/Baseline visit may not be rescreened at a later date. If results of clinical laboratory tests from the last scheduled visit of the prior double-blind phase 3 trial are not available to assess eligibility, the assessment for the affected criteria should be based on the last available measurement during the respective double-blind trial. Results from the last visit of the double-blind trial should be reviewed when they become available and action should be taken as described in [Section 3.6.2.1](#) if there are any clinically significant and/or exclusionary values.

3.5 Primary and Secondary Outcome Variables

3.5.1 Primary Outcome Variable

The primary outcome variable is the safety and tolerability of brexpiprazole, which will be assessed by examining the frequency and severity of adverse events (AEs).

3.5.2 Secondary Outcome Variables

3.5.2.1 Efficacy Variables

Efficacy variables will be as follows:

- Change from baseline in Clinical Global Impression - Severity of Illness scale (CGI-S) score;
- Mean Clinical Global Impression - Improvement scale (CGI-I) score;
- Change from baseline in Sheehan Disability Scale (SDS) score.

- Change from baseline in the Inventory of Depressive Symptomatology (Self-Report) (IDS-SR) Total Score

3.5.2.2 Safety Variables

In addition to AEs, safety variables to be examined in this trial will include physical examinations, vital signs, body weight, waist circumference, clinical laboratory tests (hematology, serum chemistry, urinalysis, and pregnancy tests), ECGs, the Simpson Angus Scale (SAS), the Abnormal Involuntary Movement Scale (AIMS), the Barnes Akathisia Rating Scale (BARS), the Columbia-Suicide Severity Rating Scale (C-SSRS), and the Massachusetts General Hospital Sexual Functioning Questionnaire (MSFQ).

Mean change from baseline and the incidence of potentially clinically relevant abnormal values will be calculated for vital signs, body weight, routine laboratory tests (including prolactin), and ECG parameters. Mean change from baseline will be calculated for coagulation parameters (prothrombin time [PT], activated partial thromboplastin time [aPTT], and International Normalized Ratio [INR]), glycosylated hemoglobin (HbA1c), thyroid-stimulating hormone (TSH), waist circumference, and body mass index (BMI; derived programmatically from body weight and height measurements). A central ECG service will be utilized to review all ECGs in order to standardize interpretations for the safety analysis. EPS will be evaluated by calculating mean change from baseline on the SAS, AIMS, and BARS. Sexual dysfunction will be evaluated as change from baseline in MSFQ score. The C-SSRS will be used to assess and classify reported suicidal behavior. By-patient listings of physical examination findings will be reviewed as a further assessment of safety.

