1.3 Known and Potential Risks and Benefits

As of 31 Dec 2010, 14 clinical trials involving brexpiprazole have been completed worldwide, including 10 in the United States (US), 1 in multiple countries (including the US), 2 in Japan, and 1 in Korea. An additional 4 trials are currently ongoing (3 in the US and 1 in multiple countries [including the US]). The collective trials can be classified as follows: four phase 1 pharmacokinetic (PK) trials in healthy subjects, 2 drug interaction trials in healthy subjects, one phase 1 PET trial in healthy subjects, one phase 1b polysomnography trial in subjects with schizophrenia, five phase 1 PK trials in specific patient populations, and six phase 2 efficacy and/or safety trials. Brexpiprazole has been well tolerated by healthy volunteers at single doses up to 6 mg and at multiple doses up to 2 mg/day. In patient trials, brexpiprazole has been well tolerated at multiple doses up to 12 mg/day in subjects with schizophrenia or schizoaffective disorder, up to 4 mg/day in subjects with MDD who received concomitant ADT, and up to 4 mg/day in adults with ADHD who received concomitant stimulant therapy.

In the 11 completed phase 1 and 2 clinical trials performed under the US IND (two phase 2 trials, one phase 1b trial, and eight phase 1 trials), 673/973 (69.2%) subjects who received brexpiprazole either alone or coadministered with another marketed medication reported at least one treatment-emergent adverse event (TEAE) compared to 158/253 (62.5%) subjects who received placebo either alone or coadministered with another marketed medication. The most common TEAEs reported for brexpiprazole in the completed trials ($\geq 5\%$ in the total brexpiprazole group and more than the total placebo group) were headache (10.6%), dizziness (8.0%), anxiety (7.1%), akathisia (7.0%), and nausea (5.5%). In the total placebo group, TEAEs that occurred in $\geq 5\%$ of subjects were headache (9.9%), insomnia (9.1%), and constipation (5.5%).

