Use of intramuscular benzodiazepines and continual use of oral benzodiazepines are prohibited throughout the trial. However, administration of specific oral benzodiazepines is permitted for the short-term management of treatment emergent AEs such as anxiety and agitation up to a maximum of 6 mg/day lorazepam (or equivalent) in divided doses. Short-acting benzodiazepines are to be used whenever possible. In countries where no short-acting benzodiazepines are commercially available, use of oral diazepam or clonazepam may be acceptable if prior authorization is obtained from the medical monitor. The following guide should be used to determine approximate lorazepam equivalents: 1 mg lorazepam = 15 mg oxazepam = 0.5 mg alprazolam = 5 mg diazepam = 0.5 mg clonazepam. The prescribed benzodiazepine should be discontinued as soon as the AE for which it was initiated subsides, as per the investigator's discretion to avoid any withdrawal effects.

Non-benzodiazepine sleep aids (ie, zolpidem, zaleplon, zopiclone, and eszopiclone only) are permitted for the treatment of insomnia, but not on the same day as administration of a benzodiazepine, regardless of indication. For the non-benzodiazepine sleep aids, sites should only utilize one of the listed medications that are approved for this indication in their respective countries and the country-specific prescribing information is to be used to determine the maximum allowable daily dose for the treatment of insomnia.

Anticholinergics are permitted for the treatment of EPS up to a maximum of 4 mg/day benztrapine or its equivalent and propranolol is permitted for akathisia or tremor up to a maximum of 20 mg three times daily (total of 60 mg/day). Sites should only utilize medications that are approved for these indications in their respective countries.

Benzodiazepines, non-benzodiazepine sleep aids, anticholinergics, and propranolol must not be administered within 12 hours prior to scheduled efficacy and safety assessments, including EPS scales. Investigators are encouraged to delay scale administration until 12 hours have elapsed, if at all possible. However, if delaying administration of efficacy and safety scales is not feasible, the scales should still be administered and the use of the medication documented, including a notation of the drug name, dose, and time of administration on the eCRF.

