7.4.5 Other Safety Data

Descriptive statistics will be provided for the SAS, AIMS, BARS, and MSFQ scales. Change from baseline in body weight will be summarized by descriptive statistics, as well as incidence of clinically significant changes in body weight. Descriptive statistics will also be provided for change from baseline in waist circumference and BMI.

Descriptive statistics will be summarized at each visit using the OC data set and at the last visit using the LOCF data set.

Suicidality monitored during the trial using the C-SSRS will be summarized as number and percentage of subjects reporting any suicidal behavior, ideation, behavior by type (4 types), ideation by type (5 types), and treatment-emergent suicidal behavior and ideation.

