9.8 Other Safety Data

Descriptive statistics will be provided for the SAS, AIMS, BARS, and MSFQ scales. Change from baseline in body weight will be summarized by descriptive statistics, as well as incidence of clinically significant changes in body weight. Descriptive statistics will also be provided for change from baseline in waist circumference and BMI.

Descriptive statistics will be summarized at each visit using the OC data set and at the last visit (Week 52/ET) using the LOCF data set.

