- CT-6.1.3 Summary of Mean Change from Baseline in Simpson-Angus Total Score (SAS) – 26-Week Enrollers
- CT-6.2.1 Summary of Mean Change from Baseline in Abnormal Involuntary Movement Score (AIMS) Total Score and Item Scores 8, 9 and 10 – All Subjects
- CT-6.2.2 Summary of Mean Change from Baseline in Abnormal Involuntary Movement Score (AIMS) Total Score and Item Scores 8, 9 and 10 – 52-Week Enrollers
- CT-6.2.3 Summary of Mean Change from Baseline in Abnormal Involuntary Movement Score (AIMS) Total Score and Item Scores 8, 9 and 10 – 26-Week Enrollers
- CT-6.3.1 Summary of Mean Change from Baseline in Barnes Akathisia Global Score (BARS) – All Subjects
- CT-6.3.2 Summary of Mean Change from Baseline in Barnes Akathisia Global Score (BARS) – 52-Week Enrollers

CT-6.3.3 Summary of Mean Change from Baseline in Barnes Akathisia Global Score (BARS) – 26-Week Enrollers

CT-6.4.1.1 Columbia-Suicide Severity Rating Scale (C-SSRS), Suicidality – All Subjects

CT-6.4.1.2 Columbia-Suicide Severity Rating Scale (C-SSRS), Suicidality – 52-Week Enrollers

CT-6.4.1.3 Columbia-Suicide Severity Rating Scale (C-SSRS), Suicidality – 26-Week Enrollers

CT-6.4.2.1 Columbia-Suicide Severity Rating Scale (C-SSRS), Suicidal Behavior by Type – All Subjects

CT-6.4.2.2 Columbia-Suicide Severity Rating Scale (C-SSRS), Suicidal Behavior by Type – 52-Week Enrollers

CT-6.4.2.3 Columbia-Suicide Severity Rating Scale (C-SSRS), Suicidal Behavior by Type – 26-Week Enrollers

CT-6.4.3.1 Columbia-Suicide Severity Rating Scale (C-SSRS), Suicidal Ideation by Type – All Subjects

CT-6.4.3.2 Columbia-Suicide Severity Rating Scale (C-SSRS), Suicidal Ideation by Type – 52-Week Enrollers

CT-6.4.3.3 Columbia-Suicide Severity Rating Scale (C-SSRS), Suicidal Ideation by Type – 26-Week Enrollers

CT-6.4.4.1 Columbia-Suicide Severity Rating Scale (C-SSRS) - Treatment Emergent Suicidal Behavior and Ideation – All Subjects

CT-6.4.4.2 Columbia-Suicide Severity Rating Scale (C-SSRS) - Treatment Emergent Suicidal Behavior and Ideation – 52-Week Enrollers

CT-6.4.4.3 Columbia-Suicide Severity Rating Scale (C-SSRS) - Treatment Emergent Suicidal Behavior and Ideation – 26-Week Enrollers

CT-6.4.5.1 Columbia-Suicide Severity Rating Scale (C-SSRS) - Listing of Treatment-emergent Suicidal Ideation – All Subjects

CT-6.4.5.2 Columbia-Suicide Severity Rating Scale (C-SSRS) - Listing of Treatment-emergent Suicidal Ideation – 52-Week Enrollers

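### SAS, AIMS and BARS are summarised only as mean change, so transient or treated EPS is diluted in the by-visit means and absent from the last-visit row if it has resolved

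*Protocol*

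**What the plan says.** For the EPS scales, Protocol 3.5.2.2 states: "EPS will be evaluated by calculating mean change from baseline on the SAS, AIMS, and BARS". The same paragraph gives other safety variables a second, subject-level summary: "Mean change from baseline and the incidence of potentially clinically relevant abnormal values will be calculated for vital signs", continuing with body weight, laboratory tests and ECG parameters.

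Protocol 7.4.5 sets the layout: "Descriptive statistics will be summarized at each visit using the OC data set and at the last visit using the LOCF data set". SAP 9.8 repeats it ("Descriptive statistics will be provided for the SAS, AIMS, BARS, and MSFQ scales"), except that it describes the final row as the "last visit (Week 52/ET) using the LOCF data set". In SAP Section 13, the planned SAS, AIMS and BARS tables (CT-6.1 to CT-6.3) are all mean-change tables, for example "Summary of Mean Change from Baseline in Barnes Akathisia Global Score (BARS) – All Subjects".

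Other relevant provisions:

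- **Schedule.** Under Protocol Table 3.6-1, SAS and BARS are rated at baseline and at seven later visits (Weeks 1, 2, 4, 8, 14, 20 and 26/ET). AIMS is rated at baseline, Week 14 and Week 26/ET.
- **Windows.** When several ratings fall in one window, SAP 11.1 keeps the last one, not the worst.
- **EPS treatment.** Protocol 4.2.1 allows anticholinergics for EPS, and "propranolol is permitted for akathisia or tremor up to a maximum of 20 mg three times daily".
- **AE tables.** SAP 9.1 tabulates EPS-related TEAEs in five categories, overall and by ADT (CT-8.8).

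**The concern.** The primary objective is long-term safety and tolerability, and Protocol 1.3 lists akathisia among the common events in the completed trials (7.0%). Clinicians rate akathisia and parkinsonism repeatedly, yet no planned scale table says how many subjects developed either.

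A group mean answers a different question. It averages a few affected subjects with many unaffected ones, and it lets improvement in some cancel worsening in others. Cancellation is a real possibility here, because baseline is the last visit of the parent trial and some subjects may arrive with EPS. Dose reduction and anti-EPS medication both make episodes shorter, and no scale analysis takes account of either.

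The scales are also the natural check on the AE count, and the plan does not use them that way. Near-zero mean changes could be read as confirming a low EPS burden when they are compatible with a material number of affected subjects.

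**Working it through.** The trial is not powered and the plan states no figure for this point, so there is nothing to reproduce. The check has two parts.

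**1. Dilution in the means**

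Inputs:
- Affected share p = 7%, borrowed from the akathisia TEAE rate in Protocol 1.3. It is an AE rate of any severity pooled over 11 phase 1 and 2 trials, not a BARS rate.
- Rise d = 3 points on the 0–5 BARS Global item, at one visit per affected subject (assumption).
- Seven post-baseline visits (Protocol Table 3.6-1).

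If episodes are shared equally over k visits, the mean change at each of those visits is p × d / k.

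| Timing of episodes | Calculation | Mean change |
|---|---|---|
| All at one visit | 0.07 × 3 | +0.21 |
| Weeks 1, 2 and 4 | 0.07 × 3 / 3 | +0.07 at each |
| All seven visits | 0.07 × 3 / 7 | +0.03 at each |
| Last visit, all resolved | – | 0 |

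Range for the seven-visit spread: 0.03 × 2 / 7 = +0.009 (3% affected, 2-point rise) to 0.15 × 3 / 7 = +0.064 (15% affected, 3-point rise).

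Cancellation: if 7% worsen by 2 points and 7% improve by 2 points, the mean is 0.07 × 2 − 0.07 × 2 = 0.

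Precision of a subject-level incidence at an assumed 7% (Wilson 95% interval):
- 210/3,000, at the protocol's enrolment ceiling: 6.1% to 8.0%.
- 90/1,280, at the SAP's ceiling: 5.8% to 8.6%.

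These counts are the assumed rate times N. They show the precision available, not an expected scale result.

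**2. Whether the AE table replaces the missing count**

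- Protocol 5.2 elicits AEs by one open, non-leading question. No text requires a raised scale score to be recorded as an AE.
- Protocol 5.1 requires a subject with two or more EPS symptoms to be entered under the single term extrapyramidal syndrome, in place of the separate symptoms.
- The akathisia category in SAP 9.1 contains akathisia, hyperkinesia and psychomotor hyperactivity. Extrapyramidal disorder sits under the parkinsonian category, and no extrapyramidal syndrome term is listed under akathisia.

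A subject with akathisia plus tremor, recorded as Protocol 5.1 directs, is therefore not counted in the akathisia category.

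The plan already uses subject-level categories elsewhere: QTc thresholds in SAP 9.4, and emergent or worsening suicidality in SAP 9.5.

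**The case against.** The best case for the plan is that EPS incidence is already covered where it belongs. The primary outcome is AE frequency and severity. EPS-related TEAEs are tabulated by category and by ADT, and TEAEs are also shown by severity and by discontinuation. Akathisia recorded once at Week 4 stays in those tables. Anti-EPS drugs appear in the concomitant-medication tables. A trained clinician also observes and questions the subject for the BARS at every treatment visit, and Protocol 5.1 asks for the specific EPS symptom on the AE page, so reporting is not purely spontaneous.

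Most of this stands, and it limits the stakes. It does not supply a scale-based count, and the recording rule in Protocol 5.1 weakens the akathisia category in particular.

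A reader might infer that early or transient EPS disappears from the scale results altogether. The documents do not support that:

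- The Week 1, 2 and 4 means are shown by parent-study treatment group (SAP 5.1), so an early cluster would be visible there.
- Subjects who withdraw early must complete the Week 26/ET evaluations, which include all three scales, and the last-visit row uses LOCF. Someone who stops because of akathisia generally carries that score into the row.
- Anti-EPS drugs are barred within 12 hours before rating. Where delay is not feasible, drug, dose and time go on the eCRF. This limits masking, although no analysis uses the record.
- Descriptive statistics could include a per-visit maximum, though the table titles name only mean change.

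It is also tempting to say that most subjects score 0. That is plausible, but neither document says so.

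A last objection concerns the remedy. A worst score rises with the number of ratings. Subjects followed for 52 weeks have up to eleven post-baseline SAS and BARS ratings, against seven for 26-week enrollers. This stands, and the fix has to allow for it.

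**Conclusion.** The point holds in a limited form. The EPS scales yield only group means, so subject-level, transient or treated EPS is diluted by visit and absent from the last-visit row if resolved. With 7% affected and a 3-point rise at one visit, the by-visit mean runs from +0.03 to +0.21 depending on how far the episodes cluster. The affected share on the scale, the size of the rise and the one-visit duration are assumptions, so this illustrates dilution and does not predict the trial's result.

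The primary AE analysis is not invalidated. What is missing is an independent, clinician-rated, subject-level check on it. That matters most for akathisia, where the recording rule and the AE grouping can lower the category count. The change should be made, because the data are already collected and the scales carry their own severity anchors.

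**What to change.** In SAP 9.8 and Section 13, keep the mean-change tables and add the number and percentage of subjects with a treatment-emergent event on the worst post-baseline rating:

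- **BARS:** Global score of 2 or more (mild or worse) with baseline below 2.
- **AIMS:** item 8 (global severity) of 2 or more with baseline below 2.
- **SAS:** distribution of the worst post-baseline change in total score. The documents give no anchor for the total score, so no cut-off is imposed.

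Use all scheduled, unscheduled and ET ratings up to seven days after the last dose (the SAP 11.1 limit), not only the last in each window.

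Present by parent-study treatment group. Restrict the pooled table and any comparison of 52-week with 26-week enrollers to the first 26 weeks, where both have the same scheduled SAS and BARS visits. State that AIMS was rated at fewer visits after Amendment 3.

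Cost: a few extra tables from existing data. The EPS figures will probably look less favourable than the mean changes. Worst-score incidence still rises with the number of ratings and has no concurrent control, so it should be read as descriptive.
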